8. REGULATORY ISSUES	9
8.1 ETHICS APPROVAL	9
8.2 CONSENT	9
8.3 CONFIDENTIALITY	9
8.4 INDEMNITY	9
8.5 SPONSOR	9
8.6 AUDITS AND INSPECTIONS	9
9. STUDY MANAGEMENT	10
10. PUBLICATION POLICY	10
11. REFERENCES	10
APPENDIX 1. SCHEDULE OF ASSESSMENTS	12
APPENDIX 2. PARTICIPANT INFORMATION SHEET (PIS)	13
APPENDIX 3. PARTICIPANT INVITATION LETTER	18
APPENDIX 4. GP LETTER	20
APPENDIX 5. CONSENT FORM	22

GLOSSARY OF ABBREVIATIONS

SDB	Sleep Disordered Breathing
OSA	Obstructive sleep apnoea
CSA	Central sleep apnoea
HFpEF	Heart Failure with preserved ejection fraction
HFrEF	Heart Failure with reduced ejection fraction
AHI	Apnoea-hypopnoea index
LVEF	Left ventricular ejection fraction

STUDY SUMMARY

TITLE Prevalence and Prognosis of Heart Failure with Preserved Ejection Fraction (HFpEF) in patients assessed for Sleep Disordered Breathing (SDB)

DESIGN Prospective observational study

- AIMS**
1. To establish the prevalence of HFpEF among patients being investigated for SDB.
 2. To examine the type and severity of SDB in patients identified with HFpEF.
 3. To characterise the phenotype of the patients that are identified with HFpEF
 4. To determine the prognosis of patients with HFpEF based on hospitalisation and mortality data.

OUTCOME MEASURES Primary Outcome measure:

- 1) Number of patients with diagnostic criteria for HFpEF

Secondary outcome measures:

- 1) The number of patients with SDB and the proportion of OSA and CSA.
- 2) Apnoea-hypopnoea index (AHI) as an indicator of SDB severity.
- 3) The frequency of cardiac co-morbidities including hypertension, coronary artery disease, diabetes and atrial fibrillation.
- 4) Rate of hospitalisation and mortality over 12 months.

POPULATION Patients referred for respiratory polygraphy at the Royal Brompton Hospital

ELIGIBILITY Patients ≥ 40 years without pre-existing treated SDB or heart failure

DURATION 20 months

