3. STUDY DESIGN

This is a prospective, observational study. The aim will be to recruit 155 patients and to collect prognostic data over a 12 month period from the participant's enrolment.

We will recruit patients referred for respiratory polygraphy, as part of their standard clinical care, at the Royal Brompton Hospital Sleep Centre. These patients would be symptomatic or be at moderate or high risk for SDB. Patients eligible will be ≥ 40 years with no history of pre-existing heart failure with reduced ejection fraction or treated sleep disordered breathing.

The patients will have a respiratory polygraphy (Embletta MPR) performed either in-hospital or at home as part of their usual care. The respiratory polygraphy involves recording nasal air flow, snore sensor, pulse oximetry, chest and abdominal movement. It is a validated for screening for sleep disordered breathing, distinguishing between obstructive sleep apnoea (OSA) and central sleep apnoea (CSA). Hypopnoea will be defined as a 30% reduction in airflow in combination with at least 3% oxygen desaturation. Apnoea will be defined as a cessation of airflow for >10 s, and in case of CSA without any thoracic or abdominal breathing effort. The apnoea-hypopnoea index (AHI) will be used to assess the severity of SDB with the following classification: Mild 5-14/h, moderate 15-30/h and severe >30 /h. Patients will be classified as OSA or CSA depending on the majority of events.

On attendance for respiratory polygraphy the following investigations will be performed:

1. Each patient will have documentation of their symptoms, medical diagnoses, medications and social history. A clinical cardiovascular examination will be performed.
2. Two symptom questionnaires will be completed. The Epworth Sleepiness questionnaire will assess daytime somnolence and is standard practice in SDB assessment. The SF-36 Questionnaire will assess indices of quality of life.
3. Biomarker assessment of heart failure will be performed by taking a single venous blood sample for plasma N-terminal-pro BNP (NT-proBNP) level and Growth Differentiation Factor-15 (GDF-15).
4. An electrocardiogram (ECG) will be carried out for documentation of cardiac rhythm.

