5. Echocardiography will be performed for assessment of structural heart disease and diastolic function in accordance to standard techniques. Parameters assessed will include: Left ventricular ejection fraction (LVEF), left ventricular diastolic function (E/A, DT, E' septal, E' lateral, E/E'), left ventricular wall thickness/mass, left atrial size and right ventricular (RV) function.

The criteria for heart failure with preserved ejection fraction will be in accordance to European Society of Cardiology guidelines as set out: Presence of symptoms and/or signs of heart failure, LVEF \geq 50%, elevated levels of natriuretic peptides, and relevant structural disease or diastolic dysfunction.

All recruited patients will be contacted by telephone at 3 monthly intervals over the next 12 months. Information recorded will include symptoms, new diagnoses, medication changes and hospitalisations. Additional data from hospital records and GP records will be used to verify the number of hospitalisations, the reason for admission and the outcome. This method will also be used to collect mortality data and if required certification information will be sought from the General Register Office.

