5.3.2 Serious AEs

An SAE form should be completed and faxed to the Chief Investigator within 24 hours. However, relapse and death due to pre-existing conditions, and hospitalisations for elective treatment of a pre-existing condition do not need reporting as SAEs.

All SAEs should be reported to the South Central-Oxford B REC where in the opinion of the Chief Investigator, the event was:

- 'related', i.e. resulted from the administration of any of the research procedures; and
- 'unexpected', i.e. an event that is not listed in the protocol as an expected occurrence

Reports of related and unexpected SAEs should be submitted within 15 days of the Chief Investigator becoming aware of the event, using the NRES SAE form for non-IMP studies. The Chief Investigator must also notify the Sponsor of all SAEs.

Local investigators should report any SAEs as required by their Local Research Ethics Committee, Sponsor and/or Research & Development Office.

Contact details for reporting SAEs

Please send SAE forms to:

**[name]
Imperial College London
National Heart & Lung Institute
[name]
London
[name]**

[contact], F.A.O. [name]

[contact] (Mon to Fri 09.00 – 17.00)

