6. ASSESSMENT AND FOLLOW-UP

We will be conducting telephone calls at 3 monthly intervals following the patient's enrolment to collect information related to the patient's health and hospitalisation history. The patient's involvement in the study will be concluded following the final telephone contact at month 12.

Any cardiovascular findings requiring follow-up will be reported to the patient's usual clinical care team and General Practitioner.

The follow-up of patients from a sleep disordered breathing perspective will be directed by their usual clinical care team.

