7. STATISTICS AND DATA ANALYSIS

The prevalence of HFpEF in this population has not previously been defined. In this study if we assume the prevalence of HFpEF to be 10% and if the precision of this estimate is within 5% then for a 95% confidence interval, the required sample size will be 139 subjects. Assuming a 10% drop out, we would require a final sample size of 155.

The primary outcome will be presented as a proportion. For the prognostic data, categorical data will be presented as frequency (percentage) and the survival pattern described using the log rank test and Kaplan-Meier survival plots.

Data and all appropriate documentation will be stored for a minimum of 10 years after the completion of the study, including the follow-up period.

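### Does leaving the prognostic event unnamed in section 7 let planned cardiac work-up pass as poor HFpEF prognosis?

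*Combined protocol and SAP*

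**What the plan says.** The Study Summary lists secondary outcome 4 as "Rate of hospitalisation and mortality over 12 months". Section 7 turns this into frequencies with percentages, and "the survival pattern described using the log rank test and Kaplan-Meier survival plots". Neither place says whether the time-to-event analysis concerns death, first admission or a combination, which groups the log-rank test compares, or which kinds of admission count.

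Four other places bear on the point:

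- Section 3 has hospital and GP records that "will be used to verify the number of hospitalisations, the reason for admission and the outcome".
- Section 5.3.2 states that "hospitalisations for elective treatment of a pre-existing condition do not need reporting as SAEs". This is a safety-reporting rule and does not define the outcome.
- Section 6 says "Any cardiovascular findings requiring follow-up will be reported" to the usual care team and the GP. It adds: "The follow-up of patients from a sleep disordered breathing perspective will be directed by their usual clinical care team".
- Section 3 has polygraphy "performed either in-hospital or at home as part of their usual care", and Appendix 1 schedules the sleep study at the baseline visit only.

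**The concern.** Prognosis is in the study title and is aim 4, so an unnamed event stands out. The study could also generate some of the events itself. Under section 3, HFpEF requires a raised natriuretic peptide together with structural disease or diastolic dysfunction. The patients labelled HFpEF are therefore those with cardiac findings to pass on. If some were then admitted for planned investigation and every admission counted, the HFpEF group would look worse because the study had examined it.

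Small numbers sharpen the worry. With a handful of HFpEF patients, one or two planned stays could double the reported percentage, and a choice made after seeing who was admitted could be steered by the result. Section 1.2 also intends to draw a screening inference from the study.

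**Working it through.** **The plan's own figure.** Section 7 assumes 10% prevalence, precision of 5 points and 95% confidence: n = 1.96² × 0.10 × 0.90 / 0.05² = 138.3, rounded up to 139. With 10% drop-out, 139/0.9 = 154.4, rounded up to 155. Both figures reproduce. They rest on prevalence alone, so the event definition does not touch them.

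**Size of the HFpEF group.** 0.10 × 139 ≈ 14, leaving 125. One HFpEF patient counted or not moves that group's risk by 1/14 = 7.1 points; one patient in the rest moves theirs by 1/125 = 0.8 points.

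**What one or two planned stays do to the estimate** (exact 95% intervals; the Fisher comparison takes an assumed 18/125 = 14% in the rest):

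| HFpEF patients counted | Risk | 95% CI | Fisher p |
|---|---|---|---|
| 2/14 | 14% | 2-43% | 1.0 |
| 4/14 | 29% | 8-58% | 0.24 |

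With 3/14 the risk is 21% (5-51%). The point estimate doubles from 2 to 4 patients, but the intervals overlap almost wholly and the comparison is inconclusive in both rows.

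**What the work-up mechanism needs.** Let b be the unplanned risk in both groups (no true difference), and let w and c be the shares with a planned cardiac stay in HFpEF patients and in the rest. All three are assumptions; the documents give none of them. The any-admission risk ratio is [1 − (1−b)(1−w)] / [1 − (1−b)(1−c)]. For b = 10%, w = 10%, c = 2%: (1 − 0.90 × 0.90) / (1 − 0.90 × 0.98) = 0.190/0.118 = 1.61.

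The rejection rates below are simulated: 139 patients, each with HFpEF at probability 0.10, exponential times, censoring at one year, log-rank test at two-sided 5%, 20,000 replicates. Each cell gives b = 10/20/30%. The last column adds an assumed 20% of planned sleep-service stays in both groups.

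| w v c | Risk ratio | Rejection | Rejection with sleep stays |
|---|---|---|---|
| 5% v 1% | 1.33/1.15/1.09 | 9.8/7.6/7.1% | 7.4/6.6/6.5% |
| 10% v 2% | 1.61/1.30/1.18 | 17.1/11.7/9.9% | 9.8/8.6/8.4% |
| 20% v 2% | 2.37/1.67/1.40 | 42.7/28.2/21.3% | 22.2/17.8/15.1% |
| 30% v 2% | 3.14/2.04/1.62 | 67.7/50.3/38.6% | 40.4/32.8/26.7% |

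The ratios in the table ignore sleep stays. Counting unplanned admissions only, rejection is 4.3-5.4% throughout. At 10% v 5%, any-admission rejection is 7-10%. With equal rates of 5% or 10% in both groups it is about 4-6%.

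The large figures therefore need a 10- to 15-fold contrast between the groups (20/2 and 30/2). At w = 5%, 0.95¹⁴ = 49% of studies would have no HFpEF patient with a planned stay at all.

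**The opposite pull.** Planned stays unrelated to HFpEF dilute a real difference. If a share p of both groups has one, a true ratio of 2.0 (20% v 10%) appears as [1 − 0.8(1−p)] / [1 − 0.9(1−p)]: 28/19 = 1.47 at p = 10%, and 52/46 = 1.13 at p = 40%. If both mechanisms operated, the net direction would be unknown.

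**Against the text.** Section 6 has findings reported; it does not say that they lead to admission rather than to outpatient or GP follow-up. It covers any cardiovascular finding, and section 3 gives every participant an ECG and an echocardiogram, so findings in the other 125 are passed on too. The in-hospital polygraphy is the baseline test, and no later sleep study is scheduled.

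**The case for a change.** The strongest case for acting is that nothing in the documents fills the gap, that the definition of HFpEF ties the group to the reported findings, and that the remedy is cheap: a few sentences and one field on the telephone form. Without a prior rule, the event could be chosen after seeing which of about 14 patients were admitted. Reading survival as death alone does not fully dispose of this, because outcome 4 still includes hospitalisation. Deaths would also say little: at 1-5% mortality, 0.99¹⁴ = 87% to 0.95¹⁴ = 49% of studies would have no HFpEF death.

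The missing definition stands. So does the arithmetic, given its inputs. What does not stand is the step from a missing definition to a biased result, because every planned-stay rate and every contrast between groups is assumed. Taken plainly, an unqualified hospitalisation rate means all admissions, which is a legitimate outcome; preferring unplanned admissions is a design choice. The worry about a late choice is fair in principle. However, the reason for admission is verified from records, so planned and unplanned stays can be told apart, and the rule fixed, before the data are analysed.

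**Conclusion.** This is missing detail in a secondary, descriptive outcome, and it does not call for a change to the plan. The event, the groups and the intervals are unstated, but the sensible filling is close at hand. All recruited patients are followed and the objective is HFpEF prognosis, so the natural comparison is HFpEF against the rest. Deaths and admissions can be described separately, with exact intervals, and the recorded reasons show how many admissions were planned.

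On size, one HFpEF patient is worth 7.1 points of risk, but the interval around 2 of 14 already runs from 2% to 43%, so the prognostic comparison will be imprecise under any event definition. With modest assumed planned stays (5% v 1%), false rejection is 7-10%. It becomes serious only under contrasts that the protocol gives no reason to expect, and it vanishes if planned stays do not occur or are equally common in both groups.

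The conclusion rests on the plan's 10% prevalence and on the absence of any described route from a reported finding to an inpatient stay. Evidence that such findings are routinely worked up by admission would reopen the point for the hospitalisation outcome. The primary prevalence estimate and the sample size of 139 (155 with drop-out) are unaffected either way.

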The phenotype of patients with SDB and those with heart failure with preserved ejection fraction (HFpEF) share similar characteristics [7]. Increasing age, hypertension, obesity, diabetes mellitus and atrial fibrillation are well recognised links in both groups. It has been shown that in patients with similar co-existent diseases, the added presence of heart failure with preserved ejection fraction results in higher morbidity and mortality rates [8].

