1.2 RATIONALE FOR CURRENT STUDY

Previous studies have evaluated the prevalence of SDB in patients known to have HFpEF, but not vice versa. Given the relationship between the two conditions and their similar phenotypes, we hypothesise that a subset of patients with unrecognised HFpEF can be identified in the population being investigated for SDB. We aim to determine the prevalence of patients with diagnostic criteria for HFpEF and examine the relationship with SDB. We will also collect prognostic data on hospitalisations and mortality over a 12 month period. This will allow inferences to be made as to whether this population should be targeted for screening for HFpEF.

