2.2 SECONDARY OBJECTIVES

- To examine the type and severity of SDB in patients identified with HFpEF.
- To characterise the phenotype of the patients that are identified with HFpEF.
- To determine the prognosis of patients with HFpEF based on hospitalisation and mortality data.

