4. PARTICIPANT ENTRY

4.1 INCLUSION CRITERIA

Patients aged \geq 40 years referred for a respiratory polygraphy at the Sleep Centre at the Royal Brompton Hospital.

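### The prognostic comparison is an unadjusted log-rank test between unnamed groups; if HFpEF patients are older than the rest, an age effect could be reported as an HFpEF effect (minor, secondary aim)

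*Combined protocol and SAP*

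**What the plan says.** Section 7 holds the whole prognostic analysis: categorical data as counts and percentages, and "the survival pattern described using the log rank test and Kaplan-Meier survival plots". No regression model, stratification, matching or covariate appears anywhere in the supplied text. The groups for the log-rank test and the event for the survival curves are not named.

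The objective served is in section 2.2: "To determine the prognosis of patients with HFpEF based on hospitalisation and mortality data". The Study Summary lists 12-month hospitalisation and mortality as a secondary outcome. Section 1.2, after describing prevalence, the relationship with SDB and the prognostic data, adds: "This will allow inferences to be made as to whether this population should be targeted for screening for HFpEF".

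On who has HFpEF, section 1.1 says of SDB and HFpEF patients: "Increasing age, hypertension, obesity, diabetes mellitus and atrial fibrillation are well recognised links in both groups". It also cites evidence that "in patients with similar co-existent diseases, the added presence of heart failure with preserved ejection fraction results in higher morbidity and mortality rates".

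Section 4.1 admits patients aged 40 or over who are "referred for a respiratory polygraphy at the Sleep Centre at the Royal Brompton Hospital", with no upper age limit.

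**The concern.** A log-rank test compares at least two groups. With an objective about HFpEF patients and follow-up of everyone recruited, the contrast most readers would expect is HFpEF against no HFpEF. Those groups are not randomised. The protocol itself links HFpEF to increasing age, and the prior evidence it cites concerns patients with similar background disease. A crude log-rank test does not make a like-for-like comparison.

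If HFpEF patients here are older, and admission and death rise with age, the test can show a difference that HFpEF did not cause. Section 1.2 intends the study to inform whether this population should be screened, so such a difference may be interpreted and not merely tabulated. The data for a simple safeguard are already held: age must be known for everyone because it decides eligibility.

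**Working it through.** **The plan's own figures.** The sample size was set for prevalence alone. Inputs from section 7: p = 0.10, half-width d = 0.05, 95% confidence.
- n = 1.96² × p(1 − p)/d² = 3.8415 × 0.09/0.0025 = 138.3, rounded up to 139. This matches.
- Dropout of 10%: 139/0.90 = 154.4, rounded up to 155. This matches.
- HFpEF patients expected at 10%: about 14 of 139, or 15-16 of 155.

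**Inputs the documents do not give.** There is no event rate, no age distribution, no age gap between HFpEF and other participants, and no hazard ratio for age or HFpEF. All of these are assumptions below.

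**Rough size of the bias.** If the hazard multiplies by h per decade and the HFpEF group is g years older, the apparent hazard ratio with no HFpEF effect is about h^(g/10).
- g = 0: 1.0 for any h.
- g = 5: 1.5^0.5 = 1.22 to 2.0^0.5 = 1.41.
- g = 10: 1.5 to 2.0.

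**Effect on the test.** Simulation with N = 155, 16 with HFpEF, no true HFpEF effect, age mean 58 and SD 10 (limits 40-95), one year of follow-up, event risk at age 58 of 5% or 20%, and 1,000 runs per scenario. Rejection at nominal two-sided 5%:

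| Age gap | Hazard per decade | Unadjusted log-rank |
|---|---|---|
| 0 years | ×1.5-2.0 | 4-5% |
| 5 years | ×1.5-2.0 | 8-13% |
| 10 years | ×1.5 | 11-17% |
| 10 years | ×2.0 | 21-36% |

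At a 10-year gap the median unadjusted hazard ratio was 1.4-1.9. With age added in a Cox model, the median was 0.9-1.0 and rejection was 3-5%. Monte Carlo error is at most about 1.96 × √(0.36 × 0.64/1000) = 3 percentage points, so the ranges should be read loosely.

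Two limits apply. Age is the only confounder in the simulation, so the adjusted estimate returns to about 1 by construction. At 5% event risk (8-11 events) some Cox fits did not converge.

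**What an adjusted estimate can deliver.** By the Schoenfeld formula, with 10% of patients in the HFpEF group, events needed for 80% power = (1.96 + 0.8416)²/(0.10 × 0.90 × (ln HR)²).
- HR 2: 7.849/(0.09 × 0.4805) = 181.5, so 182 events.
- HR 3: 7.849/(0.09 × 1.2069) = 72.3, so 73 events.
- Power for HR 2 = Φ(√(0.09 × events) × ln 2 − 1.96): Φ(−1.15) = 12% with 15 events, Φ(−0.82) = 21% with 30.

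The power calculation has no covariate. Correlation between age and HFpEF would lower these figures further.

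**The case against.** The best reply is that the aim is descriptive. The objective is the prognosis of HFpEF patients, and section 7 speaks of describing a survival pattern. Nothing promises an HFpEF effect independent of age. This stands in part: the observed event rate in HFpEF patients, at the ages they have, needs no adjustment. It does not cover the log-rank test, which is a between-group comparison, in a study meant to support a screening inference.

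Three stronger readings are tempting, and the documents do not support them.

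- A reader might infer that HFpEF and no HFpEF are the only groups the study forms. Section 3 also classifies patients as OSA or CSA, and by AHI severity. HFpEF status is the likeliest contrast, not the only possible one.
- A reader might infer that HFpEF patients are bound to be older, so that the crude test is certainly biased against HFpEF. Section 1.1 links age to both SDB and HFpEF, and everyone enrolled is referred for a sleep study at age 40 or over. The absence of an upper limit leaves room for an age gap but does not establish one. With no gap, the crude test behaves as it should.
- A reader might infer that the prognosis conclusion should rest on the age-adjusted estimate. Section 1.1 also names hypertension, obesity, diabetes and atrial fibrillation, and the evidence it cites refers to similar diseases rather than similar age. An age-only model leaves those in place, and about 14-16 HFpEF patients cannot support adjustment for all of them.

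**Conclusion.** The point holds in a conditional form. The only planned between-group prognostic method is unadjusted, its groups and endpoint are unnamed, and the protocol itself ties age to HFpEF. If there is an age gap within this cohort, a crude difference could be wrongly attributed to HFpEF.

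The size depends on assumptions about the gap, the age gradient and the event risk, none of which the documents supply. The error ranges from nothing at no gap, through roughly a doubling of the false-positive rate at 5 years, to several times nominal at 10 years with a steep gradient. Age adjustment removes the part due to age and no more. Since the comparison is weak in any case, the gain lies in preventing a misattribution, not in settling the prognosis question. Severity is minor: this is a secondary aim, and the prevalence estimate and its sample size stand.

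**What to change.** In section 7:

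1. Name the log-rank groups (HFpEF versus no HFpEF) and the endpoint (first hospitalisation or death within 12 months). If another grouping was meant, say so.
2. Keep the Kaplan-Meier curves and the log-rank test, labelled unadjusted and exploratory.
3. Report beside them a hazard ratio with 95% CI from a Cox model with HFpEF status and age as one continuous covariate, Firth-penalised if events are few.
4. State that no excess risk will be attributed to HFpEF on the crude log-rank p-value alone, and that confounding by hypertension, obesity, diabetes and atrial fibrillation remains. Diagnoses are recorded at baseline (section 3: "Each patient will have documentation of their symptoms, medical diagnoses, medications and social history"), so their frequency in each group can be tabulated for the reader.

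The cost is a few sentences and one more model, with no new data or patients. The adjusted interval will be wider than the crude one and probably inconclusive, and the report should say so.
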